4.2. Over all Survival (OS)

Overall survival is defined as the duration of time from the date of first study drug to the date of death from any cause. Subjects who are not known to have died at or prior to the database lock date will be censored at the date last known alive or database lock date, whichever occurs first.

$$\text{OS(day)} = \text{Date of death or censoring date} - \text{date of first dose of study drug} + 1$$

The date last known alive will be derived as the latest among dosing records, lab measurements, vital signs, assessment dates. The median OS and its 95% CI will be obtained using Kaplan-Meier method. Overall survival at landmark time points (e.g. 1,2,3 months and etc. from first ibrutinib date) will also be obtained from Kaplan-Meier method.

5. SAFETY

Adverse events, changes in clinical laboratory results from baseline, summary of vital signs and ECG values will be provided. All safety analyses will be based on all treated population (except for DLT evaluation which will be based on DLT population).

5.1. DLT Assessment

At the safety review meeting, DLTs will be assessed for the first 6 to 9 subjects in the DLT population. Listing of subjects for DLT assessment will be provided.

5.2. Adverse Events

Adverse events collected in the CRF (verbatim terms) by investigators will be coded to a preferred term using the Medical Dictionary for Regulatory Activities (MedDRA). The severity of adverse events is assessed in National Cancer Institute (NCI) common toxicity criteria for adverse events (CTCAE) Version 4.03.

5.2.1. Treatment-emergent Adverse Events

Treatment-emergent adverse events will be summarized by system organ class and preferred terms and by NCI toxicity grade. The same summary will be provided for treatment-related AEs, AEs leading to treatment discontinuation, AEs leading to treatment discontinuation for subjects who discontinued treatment due to AE, AEs leading to dose reduction and serious TEAEs. Adverse event overview on the incidences of all the above will be presented.

5.2.2. Adverse Events of Special Interest

5.2.2.1. Hemorrhagic Events

Bleeding events: Identified by MedDRA Hemorrhage SMQ without lab SMQ.

 pharmacyclics® An AbbVie Company	PCYC-1131-CA Statistical Analysis Plan	Page 7 of 7
--	---	-------------

Major hemorrhage: Defined as any bleeding event identified by Hemorrhage SMQ without lab SMQ that satisfies at least one of the following three criteria: Grade 3 or higher in severity, Serious AE or all grades of CNS hemorrhage.

5.2.3. Other Malignancies

Other malignancies are defined as new malignant tumors including categories non-melanoma skin cancer, melanoma skin cancer and other non-skin cancers. Both treatment-emergent adverse events of other malignancies and all other malignancies AEs reported during the study will be summarized.

5.2.4. Other Safety Observations in AE Reporting

Treatment-emergent adverse events including other cardiac arrhythmia (excluding atrial fibrillation), Interstitial Lung Disease events (ILD) and Severe Cutaneous Adverse Reactions (SCAR) will be summarized by preferred terms based on SMQ searches and/or medical monitor and safety scientist review.

Summary of treatment-emergent adverse events including leukostasis, infections, tumor lysis syndrome (TLS), cytopenias, hypersensitivity, hepatic disorders and atrial fibrillation can be obtained from existing AE summary tables.

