1.1. Study Objectives

The primary objectives are to evaluate the efficacy of ibrutinib monotherapy or in combination with either LD-AraC or azacitidine in the treatment of AML using the overall remission rate (ORR, defined as the proportion of subjects achieving a complete remission (CR) or complete remission with incomplete marrow recovery (CRI)) according to the LeukemiaNet guidelines ([Döhner 2010, Appendix 6 in Protocol Amendment 1.0](#)) and to evaluate the safety and tolerability of ibrutinib monotherapy or in combination with either LD-AraC or azacitidine in subjects with AML.

The secondary objectives are to evaluate clinical efficacy by assessing relapse-free survival (RFS), event-free survival (EFS) and overall survival (OS) and to evaluate clinical benefit defined as CR, CRI, morphologic leukemia-free state, and partial remission (PR).

The exploratory objectives are to determine the PK of ibrutinib monotherapy or in combination with either LD-AraC or azacitidine in an AML population and to evaluate prognostic and predictive biomarkers relative to treatment outcomes (ie, BTK/pBTK, secreted proteins, gene expression profiling, mutational analysis). Exploratory objectives are outside the scope of this SAP.

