5.3. Clinical Laboratory Tests

All gradable laboratory parameters will be graded using the NCI CTCAE version 4.03. A summary of worst post-baseline toxicity grade will be provided. The events with Grade 3 and 4 as the worst post-baseline toxicity grade will be also provided. Only subjects whose grades worsened are counted in the numerator of percentage calculation while the denominator is all subjects in each treatment cohort all treated population. Liver function abnormality by Hy's law will be summarized. Listing of white blood cell (WBC) count, platelet count, blood blasts (%) and abnormal cells will be presented.

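### Should Section 5.2.4 define grouped summaries for cytopenias, hypersensitivity and hepatic disorders instead of relying on the standard AE tables?

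*SAP*

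**What the plan says.** Section 5.2.4 has two tiers. Other cardiac arrhythmia, interstitial lung disease and severe cutaneous reactions "will be summarized by preferred terms based on SMQ searches and/or medical monitor and safety scientist review". For leukostasis, infections, tumor lysis syndrome, cytopenias, hypersensitivity, hepatic disorders and atrial fibrillation, the section says only that a summary "can be obtained from existing AE summary tables".

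The tables meant are those of Section 5.2.1: "Treatment-emergent adverse events will be summarized by system organ class and preferred terms and by NCI toxicity grade". The same layout is repeated for treatment-related events, events leading to discontinuation or dose reduction, and serious events.

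Hemorrhage, an event of special interest, is handled differently. Section 5.2.2.1 defines the group by a named search: "Identified by MedDRA Hemorrhage SMQ without lab SMQ".

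For laboratory data, Section 5.3 states: "A summary of worst post-baseline toxicity grade will be provided". It adds the Grade 3 and 4 events, a Hy's law summary, and listings that include white cell and platelet counts.

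**The concern.** A table of PTs counts each subject once per term and does not show which subjects appear under more than one term. A reader who wants the proportion of subjects with any cytopenia, any hypersensitivity reaction or any hepatic event cannot in general get it by adding rows, because that double counts. The largest row is only a lower bound. The worst grade across the group has the same difficulty. The SAP also names no standardised query or term list for these three topics, so the rows that make up each group are not fixed.

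Safety matters here. Section 1.1 makes it a primary objective "to evaluate the safety and tolerability of ibrutinib monotherapy or in combination with either LD-AraC or azacitidine in subjects with AML". Under Section 4.1, OS is the only protocol-defined efficacy endpoint still calculated after early termination, so safety carries most of the report. If the SAP relied on these tables for a grouped rate, the report could give a rate that is too low or too high.

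**Working it through.** The SAP gives no figure to reproduce. The check is what the tables determine, and then whether the SAP needs more.

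**Inputs.** N = 34 is the planned response-evaluable size of a combination cohort (Section 1.4), and N = 9 is the largest safety run-in (Section 1.3). The number treated per cohort is not stated. All event counts below are assumptions.

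**Step 1, PT rows alone.** For PT counts c1, ..., ck in N subjects, the number with at least one event lies between max(c) and min(sum of c, N).

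| N | Assumed PT counts | Lower bound | Upper bound |
|---|---|---|---|
| 34 | 5, 4 | 5/34 = 14.7% | 9/34 = 26.5% |
| 34 | 10, 9 | 10/34 = 29.4% | 19/34 = 55.9% |
| 34 | 5, 4, 3 | 5/34 = 14.7% | 12/34 = 35.3% |
| 9 | 2, 2 | 2/9 = 22.2% | 4/9 = 44.4% |

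**Step 2, worst grade.** Suppose PT1 and PT2 each show one Grade 2 and one Grade 3 subject. Three different data sets fit those rows:

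- Four subjects with one event each: 4 affected, two at worst Grade 3 and two at Grade 2.
- Two subjects, one with Grade 3 on both terms and one with Grade 2 on both: 2 affected, one at Grade 3 and one at Grade 2.
- Two subjects, each with Grade 3 on one term and Grade 2 on the other: 2 affected, both at Grade 3.

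So PT-by-grade rows fix neither the count nor the worst-grade split.

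**Step 3, the SOC row.** Section 5.2.1 also promises rows by SOC. If the PTs share an SOC, the upper bound becomes min(sum of c, SOC count, N). For example, with PT counts 5 and 4 and an assumed SOC count of 6, the range is 5/34 = 14.7% to 6/34 = 17.6%, not 26.5%. If the group is the whole SOC, the SOC row is the exact answer, and it gives the worst grade too if the table counts each subject once at the highest grade. The Step 1 upper bounds therefore assume that the SOC row adds nothing.

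**Step 4, what the SAP commits to.** Section 5.2.4 offers a summary of these topics, and a summary by SOC, PT and grade is what the tables provide. Neither Section 5.2.4 nor any other section announces a pooled rate or pooled worst grade for them. The higher tier in Section 5.2.4 is also summarised by PT, with no grouped row. Sections 5.2.1 and 5.2.4 agree with each other.

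**Step 5, what else is available.** Section 5.3 reports laboratory toxicity on the all treated population, which partly covers cytopenias and hepatic events. Hypersensitivity has no second source. Section 2.2 allows listings of eCRF data on request, and the coded subject-level data permit any grouping later.

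**The case for a change.** The best argument for a change is that the remedy is cheap, about three descriptive tables from data already coded, while the information lost is real. The SAP fixed a search for hemorrhage and even excluded the laboratory query, so its authors knew that term selection should be settled in advance. Cytopenias and hepatic disorders raise the same question about laboratory terms. A grouping made later would be chosen after the data were seen. Laboratory grades are not AE rates and say nothing about seriousness or discontinuation.

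Much of this stands. The tables do not in general give a grouped count, Section 5.3 is only a partial substitute, and a list chosen afterwards is weaker than one fixed beforehand.

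It does not show a fault in the SAP. The contrast with hemorrhage follows the SAP's own ranking: hemorrhage is an event of special interest, and these topics are other observations. Seriousness and discontinuation are already tabulated by SOC and PT under Section 5.2.1. The proposed rows would give these topics more than Section 5.2.4 states for interstitial lung disease or severe cutaneous reactions. Whether each topic spans several PTs or crosses SOCs cannot be settled from the SAP, so the size of the loss is not established for any of the three.

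**Conclusion.** No change is needed. The counting argument is correct within its limits: for a topic that spans several PTs and is not one SOC, the standard tables bound the number of affected subjects and leave the group's worst grade open. Followed as written, though, the SAP yields no wrong figure. PT and SOC rates are valid, no pooled rate is promised, and no test, stopping rule or conclusion depends on one. The study is open-label and non-randomized, and its reporting was scaled back after termination for lack of efficacy, so leaving lower-tier topics to the routine tables is a fair trade-off.

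The illustrated ranges, such as 14.7% to 26.5% for 5 and 4 of 34, rest on assumed counts, a planned size rather than a treated one, and no help from the SOC row. They show what could be left open, not an error in a reported result. A grouped row from a named query, chiefly for hypersensitivity, would be a convenience that the analysts may add. The only caution for the report is not to add PT counts and present the sum as a number of subjects.

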5.2.5. Deaths

Treatment-emergent adverse events leading to deaths will be summarized.

5.3. Clinical Laboratory Tests

All gradable laboratory parameters will be graded using the NCI CTCAE version 4.03. A summary of worst post-baseline toxicity grade will be provided. The events with Grade 3 and 4 as the worst post-baseline toxicity grade will be also provided. Only subjects whose grades worsened are counted in the numerator of percentage calculation while the denominator is all subjects in each treatment cohort all treated population. Liver function abnormality by Hy's law will be summarized. Listing of white blood cell (WBC) count, platelet count, blood blasts (%) and abnormal cells will be presented.
